7.6 Efficacy

7.6.1 Primary Efficacy Analysis

The primary efficacy endpoint is the change from Baseline to Study Week 12 (Study Visit 6) in log-transformed UACR. The analysis will be based on the mITT population.

The UACR values from Study Visits 2 to 7 are calculated as the mean result from 2 consecutive day mid-stream, first morning void urine samples that are submitted on the morning before and on the day of study visits. If only 1 sample is available, the measurement from that sample is used.

Baseline UACR is defined as the mean of UACR from urine samples collected on Study Visit 3 (Randomization day).

For the primary analysis of the primary efficacy endpoint, the last-observation-carried-forward (LOCF) imputation algorithm will be used, where the last recorded post-baseline value for the same subject is carried forward to the missing Study Week 12 visit.

The change from Baseline to Study Week 12 in log-transformed UACR will be analyzed in an analysis of covariance (ANCOVA) model with randomized treatment, randomization strata of sUA (<6.0 vs \geq 6.0 mg/dL) and UACR (200 to <300 mg/g vs 300 to \leq 3000 mg/g) levels as independent variables. The least square mean (LS mean), p-value, and the corresponding 95% confidence limit (CL) for the change in log-transformed UACR in each treatment group, and the difference of change in log-transformed UACR between each TMX-049 treatment group versus Placebo group will be presented. The adjusted geometric mean of Week 12 to Baseline ratio in UACR with the corresponding 95% CLs for each treatment group, and the ratio of the adjusted geometric mean of Week 12 to Baseline ratio achieved within each treatment group relative to that achieved with Placebo group with 95% CLs will also be provided.

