Statistical Methods:	
General Statistical Considerations: Data will be summarized using descriptive statistics and include mean, standard deviation (SD), median, minimum, maximum, and corresponding number of subjects (n). For log-transformed data, the geometric mean and geometric coefficient of variation will be provided. For categorical variables, the number and percent in each category will be presented. Tables will include the placebo group and each of the TMX-049 dose groups and a separate category that combines all TMX-049 dose groups.
 
Efficacy Analysis: The UACR values from the 2 consecutive day mid-stream, first-morning void urine samples that are submitted at Visits 2 to 7 will be based on the mean result of measurements in each of the paired samples. If only one sample is available, the results from that sample will be used. The change from Baseline to Week 12 (or the LOCF) in log-transformed UACR will be analyzed in an analysis of covariance model with a fixed effect for treatment, baseline log-transformed UACR and baseline serum uric acid as covariates. The least squares mean, p-value, and the corresponding 95% confidence interval (CI) for the treatment difference will be provided. The last post randomization UACR will be carried forward (LOCF) for subjects who did not have a Week 12 UACR determination. To analyze the effect of LOCF on missing data, the above analysis will be repeated using a mixed model repeated measures approach. The statistical model will feature a repeated statement and include treatment, timepoint, and treatment-by-timepoint interaction as fixed effects, baseline as a covariate, and subject as a random effect.
 
The above analysis of covariance model and repeated measures models will also be used to analyze the secondary endpoints, change in eGFR, change in UACR, change in sUA, and change in renal biomarkers at each post-treatment assessment. The proportion of subjects with >30% reduction from Baseline to Week 12 in UACR will be analyzed using a Fisher's exact test and logistic regression.
 
Renal Biomarker Analysis: Descriptive statistics will be used for renal biomarker assessment. No inferential statistical analysis will be performed for the exploratory renal biomarkers.
 
PK Analysis: PK samples that are obtained at Visits 4, 5, and 6 will be used to assess TMX-049 plasma concentrations and be used in a population PK analysis. Results will be summarized in each of the TMX-049 treatment groups.
 
Safety Analysis: Descriptive statistics will be used in assessment of all safety parameters. No inferential statistical tests will be performed using safety data. Safety analyses will be performed on the Safety Population, and safety variables, including treatment-emergent AEs, laboratory tests, vital signs, and ECGs, will be summarized.

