7.4.3.2 Randomization

Subjects who meet all eligibility criteria and who also have $\geq 80\%$ study medication compliance during the 2-week placebo run-in phase will be centrally randomized at Visit 3 to receive placebo, 40 mg TMX-049, or 200 mg TMX-049 in a 1:1:1 ratio. Randomization will be stratified by sUA (< 6.0 vs ≥ 6.0 mg/dL) and UACR (200 to < 300 mg/g vs 300 to ≤ 3000 mg/g) levels obtained at Visit 2. Randomization will be

performed through IXRS.

The randomization plan will be generated by an independent statistician and none of the Sponsor staff, Investigators, or study subjects will have access to the randomization schema prior to randomization and until the database is unblinded at the end of the study.

Prior to the start of the trial, the IXRS vendor will generate the master randomization code and a copy will be supplied to the biopharmaceutical analyst.

7.4.3.3 *Blinding*

The 2-week placebo run-in phase will be conducted in a single-blind manner. In order to ensure the subjects will remain blinded to the study treatment, the treatment packs will be identical in appearance to those used during the treatment phase.

The following controls will be employed to maintain the double-blind status of the treatment phase study:

- The placebo tablet will be identical in appearance to the TMX-049 40-mg tablet and the placebo capsules will be identical in appearance to the TMX-049 80-mg capsules.
- The treatment packs for the placebo, 40-mg dose level and 80-mg dose level will be identical in appearance. The total number of tablets and capsules making up each dose will be identical, with each subject receiving 1 tablet and 2 capsules per dose, irrespective of the treatment assigned.
- The Investigator and other members of staff involved with the study will remain blinded to the treatment and randomization code.
- Results of sUA and UACR will not be reported to Investigators, subjects, and the Sponsor staff.
- All data will be provided to [REDACTED] in a blinded manner.

7.4.3.3.1 *Unblinding in the Event of an Emergency*

All participants will be centrally randomized using an IXRS. Before the study is initiated, the directions for the IXRS will be provided to each site.

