7.10 Statistical Methods

The statistical analysis plan will be developed and finalized before database lock and will describe the selection of subjects to be included in the analyses, and procedures for accounting for missing, unused, and spurious data. Below is a summary of planned statistical analyses of the outcome measures for this study.

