7.10.4 Efficacy Analysis

7.10.4.1 *Efficacy Endpoints*

The primary efficacy endpoint for this study is:

- Change from Baseline to Week 12 in log-transformed UACR

The secondary efficacy endpoints for this study are:

- Proportion of subjects with >30% reduction from Baseline to Week 12 in UACR
- Change in eGFR (Baseline compared to each post-treatment assessment)
- Change in UACR (Baseline compared to each post-treatment assessment)
- Change in renal biomarkers (Baseline compared to each post-treatment assessment)
- Change in sUA (Baseline compared to each post-treatment assessment)

7.10.4.2 *Statistical Analysis of Efficacy*

The UACR values from the 2 consecutive day mid-stream, first morning void urine samples that are

submitted at Visits 2 to 7 will be based on the mean result of measurements in each of the paired samples. If only one sample is available, the results from that sample will be used.

The change from Baseline to Week 12 (or the LOCF) in log-transformed UACR will be analyzed in an analysis of covariance model with a fixed effect for treatment, baseline log-transformed UACR and baseline serum uric acid as covariates. The least squares mean, p-value, and the corresponding 95% CI for the treatment difference will be provided. The last post randomization UACR will be carried forward (LOCF) for subjects who did not have a Week 12 UACR determination.

To analyze the effect of LOCF on missing data, the above analysis will be repeated using a mixed model repeated measures approach and an observed case analysis. The statistical model will feature a repeated statement and include treatment, timepoint, and treatment-by-timepoint interaction as fixed effects, baseline as a covariate, and subject as a random effect.

The above analysis of covariance model and repeated measures models will also be used to analyze the secondary endpoints, change in eGFR, change in UACR, change in sUA, and change in renal biomarkers at each post-treatment assessment. The proportion of subjects with >30% reduction from Baseline to Week 12 in UACR will be analyzed using a Fisher's exact test and logistic regression.

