7.6.2 Secondary Efficacy Analysis

Secondary analysis of the primary efficacy endpoint will use mixed model repeated measures (MMRM) and all observed data. The model will include randomized treatment, randomization strata of sUA (<6.0 vs \geq 6.0 mg/dL) and UACR (200 to <300 mg/g vs 300 to \leq 3000 mg/g) levels, timepoint (Study Week), a treatment-by-timepoint interaction as fixed effects, and subject as a random effect. All post-baseline (excluding data collected at Follow-up visit) observations collected will be used in the MMRM. The MMRM statistics will be based on the restricted maximum likelihood (REML) method for estimation. An unstructured (co)variance structure will be used to model within-subject errors. The Kenward-Roger approximation will be used to approximate the denominator degrees of freedom. The adjusted mean change in log-transformed UACR from Baseline to Study Week 12 for each treatment group and the 95% CLs will be estimated in the framework of the this model, as well as the between-group difference and the 95% CLs for the difference.

Summarization of the inferential statistics will include the LS means, standard error (SE) of the estimates, p-value, and 2-sided CLs. These statistics will be provided for the within treatment group changes from Baseline and for the comparison of TMX-049 versus Placebo for the change from Baseline values. The adjusted

geometric mean of Week 12 to Baseline ratio in UACR with the corresponding 95% CLs for each treatment group, and the ratio of the adjusted geometric mean of Week 12 to Baseline ratio achieved within each treatment group relative to that achieved within Placebo group with 95% CLs will also be provided.

Figures displaying the mean change from Baseline by study week, LS mean change at Week 12 in log-transformed UACR from the ANCOVA model using LOCF, as well as the adjusted geometric mean ratio to Baseline at each study week from MMRM will be presented by treatment group.

Furthermore, the ANCOVA model specified in **Section 7.6.1** will be fitted using observed data in order to check the robustness of LOCF in the primary efficacy analysis.

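### The SAP drops the protocol's continuous baseline covariates from the primary UACR ANCOVA and the MMRM without declaring it; the test stays valid but loses precision

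*SAP*

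**What the plan says.** Protocol 7.10.4.2, and the synopsis in the same terms, analyses the change in log-UACR in an "analysis of covariance model with a fixed effect for treatment, baseline log-transformed UACR and baseline serum uric acid as covariates". It has no strata terms. The repeated-measures model in the same section has "baseline as a covariate, and subject as a random effect".

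SAP 7.6.1 says the change "will be analyzed in an analysis of covariance (ANCOVA) model with randomized treatment, randomization strata of sUA" (cut at 6.0 mg/dL) and of UACR (cut at 300 mg/g). For the MMRM, SAP 7.6.2 says "The model will include randomized treatment, randomization strata of sUA", followed by the UACR stratum, timepoint, treatment by timepoint, and subject. Neither model contains a continuous baseline value.

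Other SAP models do adjust for baseline:
- 7.6.3 adds baseline log-UACR to the 7.6.1 ANCOVA as a sensitivity analysis, in mITT and PP, with LOCF and with observed data.
- 7.6.5.1 adds baseline eGFR to the eGFR models.
- The logistic model in 7.6.5.2 has the strata plus continuous baseline UACR and sUA.

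No UACR MMRM contains baseline, and no ANCOVA of the primary endpoint contains continuous sUA. SAP Section 8, the place for changes to the planned analysis, reports none.

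The strata use "levels obtained at Visit 2" (Protocol 7.4.3.2). SAP 7.6.1, however, says "Baseline UACR is defined as the mean of UACR from urine samples collected on Study Visit 3". Protocol 7.10.2 exempts UACR from its Visit 3 baseline rule, and Protocol 7.1 and SAP 2.2 describe the Visit 2 samples as the ones that determine Baseline UACR.

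**The concern.** Noise in the baseline UACR enters the change score with a minus sign, so the change is negatively correlated with its own baseline. Conditioning on baseline removes that part of the variance. A single cut at 300 mg/g within a 200 to 3000 mg/g range, taken from an earlier visit, removes almost none of it.

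The stake is the width of the primary confidence interval, which will be wider than data already collected would allow. Sensitivity to a chance baseline imbalance is this same loss seen from another angle, not a second harm. There is also a reporting problem: the two documents name different primary models and give no reason. If the 7.6.1 and 7.6.3 results differ, a reader cannot tell why the less adjusted one leads.

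**Working it through.** **The plan's own figure.** Inputs from Protocol 7.10.1 and SAP 2.3: 40 per group, difference -0.431 (ln 0.65), SD 0.670, two-sided 0.05, two-group t-test.
- SE = 0.670 × √(2/40) = 0.1498.
- Noncentrality = 0.431 / 0.1498 = 2.88.
- Power on 78 df = 81.1% (normal approximation 82.0%), so the stated figure of more than 80% reproduces.
- Attrition: 132 × 0.9 / 3 = 39.6, about 40 per arm.

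**What a baseline covariate removes.** Adding baseline to the strata cuts residual variance by (slope of change on baseline)² × Var(baseline within strata) / Var(change). As an illustration, assume a noise SD of 0.40 per visit, a true-change SD of 0.36, and eligibility applied at Visit 2.
- Var(change) = 2 × 0.16 + 0.1296 = 0.4496, and the noise share is 0.32 / 0.4496 = 0.71.
- The slope is -0.336 and the SD of baseline within strata is 0.689.
- The cut is 0.336² × 0.689² / 0.4496 = 0.12, an SE ratio of √0.88 = 0.94.

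**Range over assumptions.** The documents give neither the noise nor the baseline-to-Week-12 correlation. Assumed:
- UACR median 700 mg/g and log SD 0.8 before the 200 to 3000 cut at Visits 1 and 2;
- sUA normal (6.3, 1.4), cut to 4 to 10, unrelated to UACR;
- true change unrelated to level;
- noise share of the change variance 0.3 to 0.9.

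The simulation used 10,000 trials per scenario, three arms of 40, and blocks of 3 in four strata. Each entry in the variance-ratio columns is the variance with the added covariates divided by the variance with strata only.

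| Noise share | Large sample, + ln(UACR), Visit 3 | n=120, + ln(UACR) and sUA, Visit 3 | 95% half-width, full model (strata-only 0.296) | Power, strata-only → full | Large sample, + ln(UACR), Visit 2 | n=120, + both, Visit 2 |
|---|---|---|---|---|---|---|
| 0.3 | 0.972 | 0.988 | 0.295 | 0.814 → 0.819 | 0.991 | 1.010 |
| 0.5 | 0.929 | 0.947 | 0.288 | 0.809 → 0.828 | 0.976 | 0.992 |
| 0.7 | 0.875 | 0.895 | 0.280 | 0.815 → 0.858 | 0.956 | 0.981 |
| 0.9 | 0.811 | 0.837 | 0.270 | 0.819 → 0.879 | 0.932 | 0.948 |

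- Strata-only type I error was 0.050 to 0.051, and the mean estimate was -0.43 in every model.
- At a ratio of 0.65 the interval is exp(-0.431 ± 0.296) = 0.48 to 0.87, and at best exp(-0.431 ± 0.270) = 0.50 to 0.85.
- Equivalent size per arm: 40 / 0.988 = 40.5 to 40 / 0.837 = 47.8.
- Adding ln(UACR) alone gave 0.979, 0.935, 0.888 and 0.827 (n=120, Visit 3), so continuous sUA costs about 1%.
- With the median at 500 to 900 and the log SD at 0.6 to 1.0, the large-sample ratio runs from 0.773 to 0.974 (Visit 3) and from 0.885 to 0.995 (Visit 2).
- The Visit 2 UACR stratum explained 0.000 of the variance of change from a Visit 3 baseline, and 0.005 to 0.029 from a Visit 2 baseline.

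**MMRM.** The calculation used Weeks 2, 6 and 12, 10% of Week 12 values missing at random, a known unstructured covariance, a common baseline slope, and 2,500 trials per scenario. Adding baseline ln(UACR) gives Week 12 variance ratios of 0.984 to 0.825 (Visit 3), a cut of 1.6% to 17.5%. With a Visit 2 baseline the ratios are 0.993 to 0.943, a cut of 0.7% to 5.7%.

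**Other assumptions.** A simpler formula, variance ratio (1 + ρ)/2 with equal variances at both visits and no strata, gives SE ratios of 0.84 to 0.97 for ρ of 0.4 to 0.9. A simulation with other noise settings gave 0.89 to 0.98, with power 0.83 to 0.89 against 0.80 to 0.82. The direction agrees; the size depends on the inputs.

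**The case against.** The best defence is that SAP 7.6.3 already fits treatment, both strata and baseline log-UACR in both populations, with LOCF and observed data. It lacks only continuous sUA, which adds nothing to precision. The protocol also says of its statistics section, "Below is a summary of planned statistical analyses of the outcome measures for this study", and leaves detail to a SAP finalized before lock. Including the stratification factors is a sound choice that the protocol omitted. On this view, only the primary label, one secondary MMRM and a disclosure line remain, and at low noise the gain is negligible.

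Much of this stands. The SAP may change the model, and the size of the gain is not anchored in the documents. The 0.000 for the Visit 2 stratum follows directly from assuming independent noise and a true change unrelated to level. The Visit 2 figures of 0.005 to 0.029 show that the cut is weak in any case. The MMRM figures ignore the cost of estimating the covariance.

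What does not stand is that 7.6.3 settles the matter. The headline interval and p-value still come from the less precise model, no UACR MMRM has baseline, and Section 8 says nothing changed.

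Two qualifications:
- The documents do not say whether 0.670 is the SD of the change or a baseline-adjusted residual SD. If it is adjusted, strata-only power would be 0.66 to 0.79 for ρ of 0.4 to 0.9.
- Dropout related to baseline in opposite directions by arm could bias observed-data models that omit baseline. An illustrative completers analysis with 10% to 12% dropout gave 0.02 to 0.05 log units. That needs an unusual dropout pattern and is not part of the main point.

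**Conclusion.** The concern holds. The protocol and SAP specify different primary ANCOVAs and different MMRMs for UACR, and the SAP declares no change. The primary test is valid and its estimate unbiased. If 0.670 is the SD of the change, it also meets the planned power.

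The cost is precision, from negligible to moderate. With a Visit 3 baseline and 120 analysed, the contrast variance is 1% to 16% larger than it need be, measured as the cut that both covariates would bring. With a Visit 2 baseline the same change ranges from +1% to -5%. These figures rest on an assumed noise share of 30% to 90%, the assumed UACR distribution, and true change unrelated to level. The difference in the text needs no assumption. It should be fixed, because the remedy is nearly free and the headline result does not otherwise benefit.

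**What to change.** - **SAP 7.6.1:** make the 7.6.3 model (treatment, both strata, Baseline log-UACR) the primary ANCOVA, and add Baseline sUA because the protocol specifies it.
- **SAP 7.6.3:** make the strata-only model the sensitivity analysis.
- **SAP 7.6.2:** add Baseline log-UACR to the UACR MMRM, in line with the protocol.
- **SAP Section 8:** list and explain every remaining departure, including the added strata terms.
- **Baseline visit:** state which visit defines Baseline UACR, and reconcile SAP 7.6.1 with Protocol 7.10.2, Protocol 7.1 and SAP 2.2. The size of the gain depends on it.
- **SAP 7.6.4 and 7.6.5.1:** these use the 7.6.1 model by reference, so say which covariates carry over.

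The cost is SAP wording before database lock and two degrees of freedom: 120 - 5 = 115 becomes 113. UACR and sUA are already collected at Visit 3 (Protocol 7.5.4.2).

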7.6.2 Secondary Efficacy Analysis

Secondary analysis of the primary efficacy endpoint will use mixed model repeated measures (MMRM) and all observed data. The model will include randomized treatment, randomization strata of sUA (<6.0 vs \geq 6.0 mg/dL) and UACR (200 to <300 mg/g vs 300 to \leq 3000 mg/g) levels, timepoint (Study Week), a treatment-by-timepoint interaction as fixed effects, and subject as a random effect. All post-baseline (excluding data collected at Follow-up visit) observations collected will be used in the MMRM. The MMRM statistics will be based on the restricted maximum likelihood (REML) method for estimation. An unstructured (co)variance structure will be used to model within-subject errors. The Kenward-Roger approximation will be used to approximate the denominator degrees of freedom. The adjusted mean change in log-transformed UACR from Baseline to Study Week 12 for each treatment group and the 95% CLs will be estimated in the framework of the this model, as well as the between-group difference and the 95% CLs for the difference.

Summarization of the inferential statistics will include the LS means, standard error (SE) of the estimates, p-value, and 2-sided CLs. These statistics will be provided for the within treatment group changes from Baseline and for the comparison of TMX-049 versus Placebo for the change from Baseline values. The adjusted

geometric mean of Week 12 to Baseline ratio in UACR with the corresponding 95% CLs for each treatment group, and the ratio of the adjusted geometric mean of Week 12 to Baseline ratio achieved within each treatment group relative to that achieved within Placebo group with 95% CLs will also be provided.

Figures displaying the mean change from Baseline by study week, LS mean change at Week 12 in log-transformed UACR from the ANCOVA model using LOCF, as well as the adjusted geometric mean ratio to Baseline at each study week from MMRM will be presented by treatment group.

Furthermore, the ANCOVA model specified in **Section 7.6.1** will be fitted using observed data in order to check the robustness of LOCF in the primary efficacy analysis.

7.6.3 Sensitivity Analysis

The analyses described in **Sections 7.6.1** and **7.6.2** will be performed using the PP population.

In addition, the primary efficacy endpoint, ie, the change from Baseline to Study Week 12 in log-transformed UACR will also be analyzed in an analysis of covariance (ANCOVA) model with randomized treatment, randomization strata of sUA (<6.0 vs ≥6.0 mg/dL) and UACR (200 to <300 mg/g vs 300 to ≤3000 mg/g) levels as independent variables, Baseline log-transformed UACR as a covariate. The least square mean (LS mean), p-value, and the corresponding 95% confidence limit (CL) for the change in log-transformed UACR in each treatment group, and the difference of change in log-transformed UACR between each TMX-049 treatment group versus Placebo group will be presented. The adjusted geometric mean of Week 12 to Baseline ratio in UACR with the corresponding 95% CLs for each treatment group, and the ratio of the adjusted geometric mean of Week 12 to Baseline ratio achieved within each treatment group relative to that achieved within Placebo group with 95% CLs will also be provided. These analyses will be performed in both mITT and PP population, using LOCF and observed data, respectively.

